Document Coversheet

Study Title: Development of a Mind Body Program for Obese Knee Osteoarthritis Patients With Comorbid Depression: Does a Mind Body Program Reduce Osteoarthritis Pain?

Institution/Site:	University of Kentucky
Document (Approval/Update) Date:	08/16/2021
NCT Number:	NCT04334278
IRB Number	67336
Coversheet created:	06/04/2024

Development of a Mind Body Program for Obese Knee Osteoarthritis Patients with Comorbid Depression

Materials and Methods

Participants and Recruitment

60 different patients will be enrolled in the feasibility RCT. Eligible patients with mild to moderate knee OA, using standard diagnostic criteria, will be referred by seven physicians at the University of Kentucky (UK) Healthcare Hip & Knee Center and the UK Healthcare Orthopedic & Sports Medicine Center during regularly scheduled office visits. Standard diagnostic criteria will include clinical examination, patient-reported symptoms/functional limitations, and radiographic assessments. In addition, because the study activities can all be completed remotely, the IRB-approved study flyer will be circulated electronically at the participating institutions as well as by patient advocate groups such as the Arthritis Foundation.

Inclusion criteria are: obesity (BMI $\geq 30 \text{ kg/m}^2$), idiopathic knee OA¹ with mild to moderate radiographic changes (Kellgren/Lawrence grade 2 or 3² or Knee injury and Osteoarthritis Outcome Scores (KOOS) consistent with knee OA³), elevated depressive symptoms (PHQ-9 $\geq 10^{4-6}$), age 45 or older^{7,8}, history of concurrent psychotropics for < 2 weeks prior to initiation of treatment or on stable doses for > 6 weeks, access to an internet-enabled computer/smart phone, willingness to comply with the study protocol and assessments, and cleared by a medical doctor to participate. Exclusion criteria are: any disorder requiring the use of systemic corticosteroids; rheumatoid arthritis; history of cancer within 5 years of screening; unable to walk/wheelchair-bound; prior surgical fixation of a femur or tibia fracture; taking high doses of opioid pain medication (>50 milligrams of morphine equivalent per day); diagnosis of a medical illness expected to worsen in the next 6 months (e.g., malignancy); active suicidal

ideation or past-year psychiatric hospitalization; non-English speaking; lifetime history of schizophrenia, bipolar disorder, or other psychotic disorder; current substance abuse or dependence (or a history within the past 6 months); practice of yoga/meditation, or other mind body techniques once per week > 45 min within the last 3 months; engagement in regular moderate or vigorous physical exercise for >30 min daily. These criteria are consistent with other clinical trials in knee OA or mind-body interventions.^{8,9} Patients with reduced or altered capacity due to administration of any mind-altering substances such as tranquilizers, conscious sedation or anesthesia, brain injury, or age outside of the targeted range will not be recruited for participation in this study.

Enrollment and baseline data collection (self-report questionnaires, blood draws, urine samples) will coincide with the patient's office visit with their treating physician and will not require an additional visit. After providing verbal consent, potential participants will meet with a research assistant for study screening. If the screening indicates that the patient meets all inclusion and exclusion criteria, study staff will begin the written informed consent process.

Eligible participants will undergo written informed consent prior to the baseline assessments. Due to the sensitive data collected in this study, patients will review and sign the combined informed consent and HIPAA-authorization if they choose to participate. The informed consent process will take place in a dedicated research room at either facility to ensure that both the patient and research team have adequate time and privacy. A specific item will be included on the Informed Consent and Data Collection Checklist Forms to ensure that "Patients were asked if they had any questions (Yes / No)." The patient will then be given the option to provide informed consent that day, to return on a different day, or opt out. Study staff will coordinate scheduling to continue the informed consent process with patients as needed. A copy

of the completed informed consent will be given to patients, added to their medical records, and documented in study progress notes.

Live Video Delivery

Participants will be recruited in-person at the University of Kentucky, but will also be recruited via electronic means at the other study sites (Massachusetts General Hospital (MGH) and Brigham & Women's Hospital (BWH)). In addition, because the study activities can all be completed remotely, the IRB-approved study flyer will be circulated electronically by patient advocate groups such as the Arthritis Foundation. The intervention will be performed remotely by the study team at MGH via live video through a HIPPA-approved software used in clinical practice at MGH for a variety of medical populations. We have extensive experience with delivery of similar mind-body programs and focus groups via live video.^{102,121} After enrollment, participants will receive an emailed link for one-click installation of the video software. A research assistant will offer participants a test call and assist with installation as needed. Participants will receive a reminder email about the appointment information and a link to access the virtual group session. The research assistant will be available to assist participants in real time with any technical challenges they may experience during the treatment sessions.

Pilot Randomized Controlled Trial

The goal of the pilot RCT is to assess the feasibility of recruitment procedures (e.g., screening, eligibility, enrollment rates), the feasibility and acceptability of the GetActive-OA and control interventions (e.g., adherence, retention), and the feasibility of data collection procedures by group (e.g., adherence, accelerometer data, blood and urine biomarker data). In line with common guidelines for feasibility studies⁴⁷, we will not test efficacy or perform between-group analyses.

We will enroll up to 60 patients with 3-8 participants per group. Participants will be randomized in a 1:1 design using a randomization scheme developed by the study statistician. The control group will have the same format and procedures as the GetActive-OA and will follow the format of the HEP.¹⁰ We will modify this program for the specific needs of patients with knee OA. Session structure is outlined in Table 3. To control for between-session practice, participants will receive an audio recording and informational handout to complete after each session. All of the patient education information, in a simplified form, will be included as an appendix in the GetActive-OA manual. We have successfully used this procedure in our clinical trial in neurofibromatosis.¹⁰

Table 3. Structure of the Health Enhancement Program to be utilized with the control group

Session	Health Enhancement Program Topics
1	Educational information on depression, obesity and knee function including the role of inflammation
2-3	Educational information on physical activity and effects on mood, weight and knee function
4-5	Educational information on nutrition
6	Educational information on sleep
7	Educational information on navigating medical care
8	Review

Analysis Plan

We will calculate descriptive statistics and report definitive feasibility and acceptability markers for the GetActive-OA, the control intervention, and the study data collection and analysis procedures. We will report feasibility as number of participants approached, screened, eligible, and enrolled. We will report number of participants who completed at least 4 out of the

6 sessions (67%). The research team's senior orthopedic researcher will assess the number of days participants wore the accelerometers at baseline and post-test using the active wear time of 8 hours/day. The research team's senior orthopedic researcher will assess the number of missing specimens (blood, urine). This will provide a realistic assessment of the study procedures as they will occur during the fully-powered efficacy trial, information on how participants might engage differently with the intervention and control, and signal of improvement in the intervention before investment of resources in the full RCT.

References

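### Does letting a KOOS score stand in for the radiographic grade leave the knee osteoarthritis entry criterion contradictory?

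*Combined protocol and SAP*

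**What the plan says.** The relevant text is in the Combined protocol and SAP, mostly under Participants and Recruitment.

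- **Referral.** "Eligible patients with mild to moderate knee OA, using standard diagnostic criteria, will be referred by seven physicians". The next sentence explains the term: "Standard diagnostic criteria will include clinical examination, patient-reported symptoms/functional limitations, and radiographic assessments".
- **Inclusion list.** Patients need idiopathic knee osteoarthritis "with mild to moderate radiographic changes". The bracket that follows gives Kellgren/Lawrence grade 2 or 3, then "or Knee injury and Osteoarthritis Outcome Scores (KOOS) consistent with knee OA", with a literature citation but no printed threshold, subscale or band. Clearance by a medical doctor is a separate requirement.
- **Screening.** A research assistant screens each patient, and written consent starts only if the patient passes the full inclusion and exclusion list. Enrollment and baseline collection coincide with the "office visit with their treating physician and will not require an additional visit".
- **Other routes.** The flyer is used "because the study activities can all be completed remotely, the IRB-approved study flyer will be circulated electronically", and under Live Video Delivery participants "will also be recruited via electronic means at the other study sites".
- **Use of the counts.** Pilot Randomized Controlled Trial makes "the feasibility of recruitment procedures (e.g., screening, eligibility, enrollment rates" a goal. The Analysis Plan reports the numbers approached, screened, eligible and enrolled.

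**The concern.** Read quickly, the section seems to define the disease twice. In the referral text, patient-reported symptoms and radiographs are parts of one list, so the first appears to be added to the second. In the inclusion bracket they are joined by *or*, so a patient-reported score can replace the film. The severity bands differ as well: grade 2 or 3 has a floor and a ceiling, whereas a KOOS consistent with osteoarthritis asks only that disease be present. A patient whose film lies outside the stated grades could seemingly enter on KOOS alone, although both statements speak of mild to moderate disease.

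The count of eligible patients is itself a result of this pilot. If two members of staff could each follow the protocol and classify the same patient differently, that count would lack a single meaning to carry into the efficacy trial.

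**Working it through.** The plan gives no figure to reproduce. The check is a reading of the text, followed by an enumeration of cases.

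**Step 1: what each statement governs.** The diagnostic sentence directly follows the one on physician referral. It lists what the work-up covers and names radiographic assessment as a modality, without setting a grade. The inclusion list is what the research assistant applies before consent. A work-up that includes films is compatible with an entry rule that accepts either a grade or a KOOS result, so the two statements do not compete for the same job.

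**Step 2: which patients the wording leaves open.** Cross film status (3 levels) with KOOS (2 levels): 3 × 2 = 6 profiles. Compare the bracket read literally with the bracket read under its mild-to-moderate radiographic heading, so that a film showing otherwise excludes the patient.

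| Film | KOOS consistent | Literal *or* | Heading limits the bracket |
|---|---|---|---|
| Grade 2 or 3 | yes | in | in |
| Grade 2 or 3 | no | in | in |
| Outside 2 or 3 | yes | in | out |
| Outside 2 or 3 | no | out | out |
| None | yes | in | in |
| None | no | out | out |

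The literal rule admits 2 + 1 + 1 = 4 profiles and the heading-limited rule admits 3. They differ on one: a film outside the range with a consistent KOOS. The printed *or* itself admits the patient with no film and a consistent KOOS, which suits recruitment by flyer and electronic means, where no radiographic step is described.

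**Step 3: stricter rules.** Requiring an in-range film from everyone would admit 2 profiles and differ from the literal rule on 2. Requiring both film and KOOS would admit 1 and differ on 3. The size of the supposed conflict therefore depends on which rival rule is assumed. Neither stricter rule is stated: the diagnostic sentence sets no grade, and the bracket says *or*. None of these counts is a share of patients.

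**Step 4: what depends on the answer.** Pilot Randomized Controlled Trial excludes efficacy testing and between-group analysis. The target of 60 rests on no power calculation. The Analysis Plan is descriptive. Under any one consistently applied reading, the screened, eligible and enrolled counts are well defined.

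**The case for a change.** The strongest contrary case is that eligibility is a reported outcome here, so an unclear entry rule affects a result. A deliberate remote route would explain the patient with no film, but not the one whose film is out of range. The protocol never restricts the KOOS limb to remote recruits, and the enrollment text places enrollment at an office visit. The citation cannot be relied on to fill the gap, because the protocol prints no threshold and a cited definition would not say whether KOOS adds to or replaces the film. The other safeguards, idiopathic disease and medical clearance, set no severity limit.

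Much of this stands as a comment on drafting. The bracket is awkward, no KOOS threshold is printed, and one profile is unsettled. What does not stand is the step to an unreliable count. The documents describe one list applied at screening. They do not describe separate teams working to different standards for referred and electronic recruits. The claim that the KOOS limb has no upper severity limit also goes too far, since mild to moderate appears both in the bracket's heading and in the referral sentence. The supportable statement is narrower: no limit is printed for the score itself. Reporting counts by qualifying route would be informative, but it is a preference, and no stated objective needs it.

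**Conclusion.** The concern does not call for a change. The two statements differ in purpose rather than conflict, and what remains is a missing detail of eligibility wording: one of six film-by-KOOS profiles is unsettled, in a number of patients the documents do not allow to be estimated. No test, sample size, analysis or stated figure moves.

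This rests on two assumptions: that screening staff apply a single reading throughout, and that the report states the entry rule as it was used. Both are ordinary practice, and nothing in the documents suggests otherwise. If different readings had in fact been applied on different recruitment routes, the eligible count would mix two definitions and would need that caveat when used to plan the efficacy trial. Which reading is clinically right is for the sponsor and is not judged here.

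### Acceptability of both programmes is an aim, but the Analysis Plan designates no acceptability marker, leaves retention undefined, and specifies no participant rating or measure of home practice

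*Combined protocol and SAP*

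**What the plan says.** Under Pilot Randomized Controlled Trial, one goal of the pilot is to assess "the feasibility and acceptability of the GetActive-OA and control interventions (e.g., adherence, retention"). A further goal is "the feasibility of data collection procedures by group (e.g., adherence, accelerometer data, blood and urine biomarker data"). The same section rules out efficacy testing and between-group analyses.

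The Analysis Plan promises to "report definitive feasibility and acceptability markers for the GetActive-OA, the control intervention, and the study data collection and analysis procedures". Its specific outputs are:

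- recruitment flow: "We will report feasibility as number of participants approached, screened, eligible, and enrolled";
- session completion: "We will report number of participants who completed at least 4 out of the" 6 sessions, given as 67%;
- a researcher will "assess the number of days participants wore the accelerometers at baseline and post-test using the active wear time of 8 hours/day";
- the same researcher will "assess the number of missing specimens (blood, urine").

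It closes by saying that these results will show, among other things, how engagement may differ between intervention and control ahead of the full trial.

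On work between sessions, the text before Table 3 says: "To control for between-session practice, participants will receive an audio recording and informational handout to complete after each session". No log, diary or other record of use is described.

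Self-report questionnaires appear once, under Participants and Recruitment, as part of baseline data collection. Their content is not listed.

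**The concern.** The plan gives feasibility an operational meaning and gives acceptability none. The reader has to infer that session completion is meant to serve, because nothing else in the Analysis Plan describes how participants took to either programme.

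Attending a scheduled video group is a reasonable behavioural sign of acceptability, but a partial one. It also depends on timetable and technology, and someone can attend 4 sessions without finding them useful. Supplying a recording and a handout matches what participants are given. It does not show what they used, so the statement that practice is controlled cannot be checked from any specified output.

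The pilot tests no efficacy, so these descriptive markers are its main product. Ratings and practice that are not collected while participants are in the trial cannot be recovered afterwards. Two arms with the same attendance but different perceived value or home use would look alike in the specified report, although differential engagement is one of the things the plan says it will describe.

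**Working it through.** **Step 1. Match each Analysis Plan output to what it measures.**

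| Output | What it measures | Participant's view of the programme? | Home practice? |
|---|---|---|---|
| Numbers approached to enrolled | Recruitment | No | No |
| At least 4 sessions completed | Attendance | Indirectly | No |
| Accelerometer wear days | Data collection | No | No |
| Missing blood or urine specimens | Data collection | No | No |

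One of the four bears on engagement with a programme. None is a rating and none records practice.

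**Step 2. Compare the aims with the outputs.** The aims give adherence and retention as examples of feasibility and acceptability. Session completion can be read as adherence. Retention has no definition (retained to what point, on which assessment) and no line in the Analysis Plan. No threshold for calling either programme acceptable is given.

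**Step 3. Reproduce the plan's own figure.** 4/6 = 66.7%, which rounds to the stated 67%. Table 3 lists 8 sessions for a control said to share the format of GetActive-OA. Against 8 sessions, 4/8 = 50%. Two-thirds of 8 is 5.3, so at least 6 sessions would be needed to reach that proportion. The same count of 4 therefore means 67% or 50%, depending on which session total applies.

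**Step 4. What attendance alone leaves open.** Up to 60 participants at 1:1 gives up to 60/2 = 30 per arm. Let A be the number completing at least 4 sessions. The number who did so and also rated the programme favourably, or practised at home, lies between 0 and A. Attendance gives no tighter bound.

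- Assumed A = 24 of 30 (80%): the joint number lies between 0 and 24, that is 0% to 80% of the arm.
- Assumed A = 20 of 30 (67%): between 0 and 20, that is 0% to 67%.
- If A = 24 in both arms, the specified report shows no difference, while the difference between arms in the joint number could be anything from -24 to +24.

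The values of A are assumptions; the documents forecast no attendance.

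**Step 5. Sampling precision, for context.** The exact (Clopper-Pearson) 95% interval is 61% to 92% for 24/30 and 47% to 83% for 20/30. Even attendance will be estimated loosely at this size. The gap described here is a separate matter: it concerns what is measured, and more participants would not close it.

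The point is about an unspecified measure, so adding one yields no corrected figure.

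**The case against.** The strongest reply is that the protocol indicates what it means by acceptability, namely behavioural markers such as adherence and retention, and that preferring rating scales is a matter of taste in a descriptive pilot. Part of this stands. Behavioural markers are legitimate, and no statement in the documents requires a rating. What remains is that the plan promises definitive markers, designates none for acceptability, and drops one of its own two examples on the way to the Analysis Plan.

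Three stronger readings are tempting and should not be adopted.

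- *Attendance is the only marker available by arm.* Retention is named for both interventions, and adherence, accelerometer and specimen data are to be assessed by group. The attendance sentence does not itself say it is split by arm; that follows only from the promise of markers for each intervention. However, retention is undefined and the by-group items are listed under data-collection feasibility, so they do not close the gap.
- *No rating or practice data are recorded.* This would be an inference from silence. Questionnaire content is not listed and adherence is not defined. The text also cites references numbered beyond its own list and has a Table 3 without Tables 1 and 2, so it may be an extract. What can be said is that none is specified here.
- *The full trial would go ahead with a control that participants do not find credible.* The documents state no progression rule and do not say that the control must match GetActive-OA in credibility. They do not give the content of GetActive-OA or how much home practice it expects.

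**Conclusion.** The point holds as a gap in specification. Acceptability is an aim with promised definitive markers, yet the Analysis Plan designates no marker for it. Its one engagement output is completion of at least 4 sessions, retention is not carried over, and neither a participant rating nor a practice measure is specified. The pilot as written therefore answers its acceptability and differential-engagement questions only in part.

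The size cannot be put as a single number. Attendance leaves the share who attended and also valued or practised the programme anywhere between zero and the attendance rate. This rests on reading the listed outputs as the complete set. If the unlisted questionnaires already hold suitable items, the remedy reduces to naming them.

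This does not invalidate the pilot or affect participant safety. It is an inexpensive improvement worth making while data can still be collected. The difference between 6 sessions in the marker and 8 in Table 3 is a separate inconsistency; the documents do not show which total is intended.

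**What to change.** In both arms:

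1. **Rating.** Add a short electronic satisfaction and credibility form at post-test, sent also to those who stop attending. Name it in the Analysis Plan as an acceptability marker. Report it descriptively by arm, with the number responding, alongside adherence and retention, and define retention. Descriptive reporting by arm is consistent with the decision not to run between-group analyses.
2. **Practice.** Add one electronic item per session asking on how many days the recording or handout was used since the previous session, and report its distribution by arm. Alternatively, reword the practice sentence so that it claims only matched materials.
3. **If such items already exist** among the self-report questionnaires, name them as the acceptability and practice outputs instead of adding new ones.

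Separately, reconcile the 6-session marker with the 8 control sessions in Table 3, and state the denominator used in each arm.

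Cost: one short form and one item per session, which fits the remote conduct of the study. Participants give a few minutes, and someone must send the form to those who have stopped attending. Self-reported practice is imprecise, and response among non-attenders may be low, which is why the number responding should be shown.
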